### 8.0 Statistical Analysis Plan and Sample Size Justification

The primary and secondary objectives and endpoints are in Section 2. The accrual goal for this trial is 35 participants evaluable for both safety and efficacy.

### 8.1 Evaluability

### 8.1.1 Evaluability for Safety

Participants will be evaluable for safety if they receive a minimum of 75% of the first cycle of ivosidenib and have received one dose of nivolumab, unless they experience a DLT. The DLTwindow will be defined as from first dose through completion of the first 28-day cycle.

### 8.1.2 Evaluability for Efficacy

Patients will be evaluable for the co-primary efficacy objectives of response and PFS at the time of first radiographic assessment at week 12 of the study. Patients must receive a minimum of 75% of the first cycle of ivosidenib and have received one dose of nivolumab to be considered evaluable. Any patient having taken 75% of ivosidenib with clear clinical progression prior to first restaging at will also be evaluable for this objective.

### 8.2 Statistical Analysis Plan

# 8.2.1 Primary Objective: Efficacy

Given that the response rate would be expected to be< 10% and PFS < 3.5 months in this patient population of IDHI mutant advanced solid tumors or gliomas, we will consider a participant to have had a positive outcome if they have a positive PFS6 (PFS6 is scored as either No or Yes) *and* they have had at least a partial response (evaluated by RANO in glioma patients and RECIST in patients with solid tumors) at the 12 week scan.

An Optimal Simon two-stage design is employed, where a probability of positive outcome less than 0.1 would not be promising and a probability of positive outcome 0.3 would warrant further interest. In the first stage, 18 participants will be accrued. If three or more participants have positive outcomes, 17 more participants will be accrued. If 7 or more out of the 35 participants have positive outcomes, the null hypothesis p<0.1 will be rejected at a=0.05. This design has 90% power if p > 0.3.

For all tumor types, six-month progression-free survival (PFS6) is defined as survival to six months after the initiation of treatment without objective tumor progression

The probability of positive outcome and 95% confidence interval will be estimated using the method of Koyama and Chen (Koyama and Chen 2008).

# 8.2.2 Secondary Objective: Safety

Summary tables and listings for adverse events will include treatment-emergent adverse events (AEs), where AE is defined as any AE that occurred between the first dose of any study drug and 28 days following the last dose of any study drug. The incidence of AEs (new or worsening from baseline) will be summarized according to the Medical Dictionary for Regulatory Activities (MedDRA) by system organ class and/or preferred term, severity (based on NCI CTCAE vS.0 grading as assessed by the Investigator), seriousness, and relation to study treatment. All tabulations will be accompanied by probability of events and exact (Clopper-Pearson) 95% confidence intervals. The following summaries will be produced:

- All AEs
- AEs leading to dose modifications
- Treatment-related AEs
- Grade 3 or higher AEs
- Grade 3 or higher treatment-related AEs
- The most commonly reported AEs (ie, those events reported by 10% of all participants)
- SAEs
- Discontinuations due to AEs

By- participant listings will be provided for on-treatment deaths (on-treatment is defined as the period starting from the first dose to 100 days after the last dose), AEs, SAEs, and AEs leading to discontinuation of treatment.

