# 4.4.1 Withdrawal from Study Treatment

Participants may discontinue or be discontinued from study treatment at any time. In this situation, a participant without documented progressive disease by the treating investigator should be followed for tumor assessments until the development of progressive disease and/or survival. Participants will be discontinued from study treatment for the following reasons:

- Grade 4 QTcF prolongation.
- Disease progression (participants who are, in the opinion of the treating investigator, benefiting from treatment [e.g., slow progression or immune-related response evaluation] may be allowed to continue on study treatment)
- Severe or unacceptable toxicity
- Death
- Lead Investigator decision
- Subject decision to withdraw from treatment
- Protocol violation: non-adherence to study treatments as required for evaluability (detailed in section 8.1.1) or other protocol requirements.
- Confirmed pregnancy (study therapy should be immediately interrupted based upon a positive urinary human chorionic gonadotropin [hCG] test, and permanently discontinued if confirmed by a serum -hCG test)
- Lost to follow-up

All AEs should be followed until resolution or for a period of 28 days from the last dose of study treatment, whichever is shorter. If the participant withdrew from treatment because of an AE, every

effort must be made to perform protocol-specified safety follow-up procedures. All SAEs that occur up to 100 days post last dose of nivolumab must be reported to BMS World Wide Safety.

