### Adverse Event Reporting Period

Investigators will seek information on AEs at each participant contact, as outlined below. All AEs, whether reported by the participant or noted by study personnel, will be recorded in the participant's medical record.

After informed consent has been obtained but prior to initiation of study drug, only SAEs caused by a protocol-mandated intervention should be reported (e.g., SAEs related to invasive study procedures such as biopsies).

After initiation of study drug, all AEs and SAEs regardless of attribution will be collected at every visit until 100 days following the last administration of study treatment or until study discontinuation/termination or until initiation of subsequent anticancer therapy, whichever occurs first. Participants will be assessed at the Follow-up Visit to determine if any new AEs have occurred. After this period, Investigators should report only SAEs that are considered to be related to study treatment.

All Serious Adverse Events (SAEs) that occur following the participant's first does of study treatment through 100 days of discontinuation of dosing must be reported to according to section 7.3, whether related or not related to study drug.

Following the participant's first dose of study treatment, all SAEs, whether related or not related to study drug, are collected, including those thought to be associated with protocol-specified procedures. The investigator should report any SAE occurring after these aforementioned time periods, which is believed to be related to study drug or protocol-specified procedure.

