# 7.2.2 SAE Reporting

All events meeting the definition of a serious adverse events, which occur after the date of first dose of study treatment and within 100 days of the last dose of study treatment, should be reported according to the departmental SAE checklist and SAE form. The initial SAE form should be sent to the following within 1 business day of the Principal Investigator becoming aware:

- 1. Sponsor-Investigator: [name], [contact]
- 2. [contact]
- 3. Local Institutional Review Board when reporting requirements are met.
- 4. BMS SAE Email Address: [contact] or [contact]
- 5. Servier SAE Email Address: [contact]

In addition to completing appropriate patient demographic and suspect medication information, the report should include as applicable the following information that is available at the time of report within the Sections Band C of the departmental SAE form:

- CTCAE term(s) and grade(s)
- current status of study drug
- all interventions to address the AE (testing and result, treatment and response)
- hospitalization and/or discharge dates
- event relationship to study drug

Pregnancies and overdoses must also be reported and submitted as instructed above.

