### 7.4 Follow-up of Participants after AEs

### 7.4.1 Investigator Follow-Up

The Investigator should follow each AE until the event has resolved to baseline grade or better, the event is assessed as stable by the Investigator, the participant is lost to follow-up, or the participant withdraws consent. Every effort should be made to follow all SAEs considered related to study treatment or trial-related procedures until a final outcome can be reported.

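### AE tables and listings in 8.2.2 stop 28 days after the last dose, while AEs and SAEs are collected, and deaths listed, for up to 100 days; onsets on days 29-100 have no stated place in the AE summaries.

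*Combined protocol and SAP*

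**What the plan says.** Five places in the combined protocol and SAP set a post-treatment window for adverse events.

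- **8.2.2, tables and listings.** The section opens "Summary tables and listings for adverse events will include treatment-emergent adverse events (AEs" and defines the events concerned as "any AE that occurred between the first dose of any study drug and 28 days following the last dose of any study drug". The summaries that follow include SAEs, Grade 3 or higher AEs and treatment-related AEs, each with an exact 95% interval.
- **8.2.2, death listing.** For deaths, "on-treatment is defined as the period starting from the first dose to 100 days after the last dose".
- **7.0, Adverse Event Reporting Period.** After study drug starts, "all AEs and SAEs regardless of attribution will be collected at every visit until 100 days following the last administration of study treatment". Collection stops sooner at study discontinuation or termination, "or until initiation of subsequent anticancer therapy, whichever occurs first".
- **7.2.2, SAE reporting.** SAEs are reportable when they occur "within 100 days of the last dose of study treatment".
- **4.4.1 against 7.4.1, follow-up of existing events.** Section 4.4.1: "All AEs should be followed until resolution or for a period of 28 days from the last dose of study treatment, whichever is shorter". Section 7.4.1: "The Investigator should follow each AE until the event has resolved to baseline grade or better", or until it is judged stable, the participant is lost, or consent is withdrawn.

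**The concern.** The analysis window is narrower than the collection window, and the plan neither explains the gap nor says where the remaining events will be reported. Safety of the combination is a stated secondary objective (2.1.2). Nivolumab is infused every 28 days (3.1), so the table window after the last dose is no longer than one dosing interval. The protocol elsewhere treats 100 days as the period over which serious events still have to be reported.

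With at most 35 participants, a few first events after day 28 would visibly lower the reported SAE, Grade 3+ and treatment-related rates. The Clopper-Pearson intervals cannot correct for events that were never counted. The same section could also give two different accounts of one participant, depending on which output is read.

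**Working it through.** There is no sample size, power or alpha figure to reproduce here. The check sets the windows side by side and then asks what can be said about size.

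**1. Inputs.** Table window T = 28 days after the last dose of any study drug (8.2.2). Maximum collection window C = 100 days (7.0, 7.2.2). Death-listing window = 100 days (8.2.2). Maximum sample = 35 (8.0).

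**2. Days excluded.** C − T = 100 − 28 = 72 days (days 29-100), or 72/100 = 72% of the maximum post-treatment window.

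**3. Trace one event.** Both drugs have stopped and no new anticancer therapy has begun. A fatal AE starts on day 60 and death occurs by day 100.
- 7.0 and 7.2.2: collected and reported, since 60 ≤ 100.
- 8.2.2 death listing: included, since death falls within 100 days.
- 8.2.2 SAE, Grade 3+ and, if attributed, treatment-related tables: excluded, since 60 > 28.

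**4. Days are not events.** The documents give no post-treatment AE rate or onset pattern, so the share of post-treatment events excluded depends entirely on assumptions.

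*Declining onset (assumed), half-life h days, collection to day 100:* excluded share = 1 − (1 − 2^(−28/h)) / (1 − 2^(−100/h)).

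| h (days) | 7 | 14 | 28 | 42 | 84 |
|---|---|---|---|---|---|
| Share excluded | 6% | 25% | 45% | 54% | 63% |

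The share passes 50% only when h exceeds about 34 days.

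*Uniform onset (assumed), collection ending on day c because of new therapy or study discontinuation:* excluded share = (c − 28)/c.

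| c (day) | 28 | 42 | 56 | 70 | 100 |
|---|---|---|---|---|---|
| Share excluded | 0% | 33% | 50% | 60% | 72% |

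The range across these assumptions is 0% to 72%.

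**5. Effect on a table row (assumed counts).** If k of 35 participants have their first event of a given type on days 29-100, the row is low by k/35: 2.9 percentage points for k = 1, 5.7 for k = 2, 8.6 for k = 3, and none for k = 0. For example, with 4 participants already counted and k = 3, the table shows 4/35 = 11% (exact 95% CI 3-27%) where the 100-day count is 7/35 = 20% (8-37%). A participant with an earlier event of the same type adds nothing to k.

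**The case against.** An analysis window shorter than the collection window is a legitimate choice, and 28 days matches the scheduled safety follow-up visit at day 28-33 (3.1, 6.1). That stands: the 28-day tables are not wrong in themselves. What is missing is any stated home for later events. The remark in 8.2.2.2 that further safety analyses may be done commits to nothing.

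A second objection concerns data quality. Section 6.1 treats the day 28-33 visit as the final safety assessment. Under 3.1, participants who stop for progression do not enter PFS follow-up. The 100-day footnote to Table 3 covers SAEs only. Capture of non-serious AEs after that visit will therefore be uneven and related to the reason for stopping. This also stands. It is why a reader who inferred that the main definition must be replaced by a 100-day one would go too far: every AE table would then mix scheduled with largely unscheduled ascertainment.

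Third, one could read the 100-day on-treatment definition in the listing sentence of 8.2.2 as covering the AE and SAE listings as well as deaths. That would conflict with the section's opening sentence, and the summary tables would still stop at 28 days.

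Fourth, no decision depends on these tables. The toxicity rule uses Cycle 1 DLTs (7.5, 8.2.4), and the primary analysis is efficacy. That is correct, and it limits the consequence to completeness of the secondary safety results.

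**Conclusion.** The mismatch is in the text. AEs and SAEs with onset on days 29-100 after both drugs stop are collected but have no stated place in the AE summaries. Its size is up to 72 of 100 post-treatment days, fewer where collection ends early. The number or share of events lost cannot be derived from the documents.

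Four stronger readings are tempting and not supported:

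- **That most late events are lost.** The 72% is a share of days. The share of events ran from 0% to 72% under the assumptions tried.
- **That every safety summary is affected.** The death listing runs to 100 days. The AE-over-time tabulation in 8.2.3 restates no 28-day limit. The laboratory, vital-sign, ECOG and QTcF summaries do not use this definition, and DLT is confined to Cycle 1.
- **That late events after nivolumab are generally dropped.** The clock runs from the last dose of any study drug. Nivolumab ends by 1 year while ivosidenib may continue indefinitely (3.1), so events in participants still on ivosidenib stay in the tables.
- **That 4.4.1 will leave outcomes unknown.** Its sentence concerns how long an existing event is followed, not which onsets are counted, so incidence is unaffected. It conflicts with 7.0 and 7.4.1, and with the SAE follow-up text under 7.2.2, but the documents do not say that 4.4.1 prevails.

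**What to change.** 1. Keep the 28-day treatment-emergent tables. Add to 8.2.2 a summary and by-participant listing of SAEs, Grade 3 or higher AEs and treatment-related AEs from first dose to 100 days after the last dose of either drug, or to the start of subsequent anticancer therapy if earlier.
2. State in 8.2.2 which window each table and listing uses, so that the treatment-emergent and on-treatment periods cannot be confused.
3. Note with the new table that capture of non-serious AEs is less complete after the day 28-33 visit, and that collection ends early for some participants.
4. Reconcile the 4.4.1 follow-up sentence with 7.0, 7.2.2 and 7.4.1, so that one rule governs how long an ongoing event is followed.

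The cost is SAP wording and one extra table cut; 7.0 and 7.2.2 already call for the data. The 100-day table will contain more disease-related background events, and its non-serious entries should be read with the caveat in item 3. The primary analysis, the Simon design and the DLT stopping rule are unaffected.

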### 8.2.2.1 Laboratory Abnormalities

For laboratory tests included in the NCI CTCAE version 5.0, laboratory data will be graded accordingly; a Grade 0 will be assigned for all non-missing values not graded as 1 or higher. For laboratory tests where grades are not defined by NCI CTCAE, results will be graded by the low/normal/high classifications based on laboratory normal ranges.

The following summaries will be generated separately for hematology, serum chemistry and coagulation studies, and urinalysis laboratory tests:

- Descriptive statistics for the actual values and/or change from baseline of clinical laboratory parameters over time.
- Shift tables using NCI CTCAE grades to compare baseline to the worst on-treatment value (for laboratory tests where NCI CTCAE grades are not defined, shift tables using the low/normal/high/[low and high] classification to compare baseline to the worst on-treatment may be generated).
- Listing of all laboratory data with values flagged to show the corresponding NCI CTCAE grades and the classifications relative to the laboratory normal ranges.

# 8.2.2.2 Other Safety Data

- Descriptive statistics for the actual values and/or the changes from baseline of vital signs (including systolic and diastolic blood pressure, heart rate, respiratory rate, and temperature) over time will be summarized.
- Descriptive statistics of ECOG PS over time will be summarized by frequency. Shift tables

may be provided for ECOG PS from baseline to worst value of post-baseline assessments.

- Categorical analysis of QTcF intervals may be performed. Maximum QTcF intervals and maximum changes from baseline may also be summarized similarly in a separate display. ECG abnormalities if collected will be presented in a data listing.
- Additional safety analyses may be performed if deemed necessary.

# 8.2.3 Secondary Objective: Longitudinal Clinical Outcomes

The distribution of adverse events over time (during and after Cycle 1) will be tabulated and described graphically. Surviving participants without progression will be censored as of the date of the last negative examination. Progression-free survival, defined from the beginning of treatment as survival without objective tumor progression, up until 18 months after the last efficacy-evaluable participant has initiated treatment will be characterized by the product-limit (Ka-plan-Meier} method with a 95 confidence region.

# 8.2.4 Exploratory Objective: Biomarkers and Response to Treatment

DLT (defined in Section 7.5) will be monitored throughout the trial and a stopping rule will be evaluated after every five participants have started Cycle 1. If the number of participants experiencing DLT equals or exceeds the number specified in the following table, the trial will be paused and the dosing reconsidered:

# Participants	# DLTs
5	3
10	5
15	7
20	8
25	10
30	12

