Number of Participants	Eighteen in the first stage and seventeen in the second stage, for a maximum of 35 patients
Investigational Product	lvosidenib, Nivolumab, route of administration: intravenous (IV) and oral (po), respectively
Estimated average treatment duration per patient	6 months
Duration of Participation	Up to 2 years
Reference therapies	Ivosidenib or Nivolumab
Statistical Methodology	An optimal Simon two-stage design is employed, where the primary endpoint is a composite of response (RANO for glioma patients or RECIST for solid tumor patients) and PFS6. Dose-limiting toxicity (DLT) is monitored throughout the trial using a Bayesian beta-binomial model. In secondary objectives, adverse events, response over time and progression-free survival are assessed. In exploratory objectives, the relationship between baseline biomarkers and response are described.
Safety Evaluations	Physical examination and ECOG performance status, vital signs, safety laboratory assessments (Hematology, chemistry, thyroid studies, pregnancy test (all women of child-bearing potential [WOCBP]) must have a negative pregnancy test to be eligible. Pregnancy testing to be done every $4 \pm 1$ weeks while on study treatment), AEs.
Data and Safety Monitoring Plan	Investigator/sub-investigators, regulatory, CRS management, clinical research coordinators, clinical research associates, data managers, and clinic staff meet regularly in disease center Data Safety Monitoring Boards (DSMB) to review and discuss study data to include, but not limited to, serious adverse events, participant safety issues, recruitment issues, accrual, protocol deviations, unanticipated problems, breaches of confidentiality Minutes of the disease center DSMB meetings are available to those who are unable to attend in person. A formal, sequential decision rule based on dose-limiting toxicity will be evaluated after every five participants have completed Cycle 1.

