# 8.3 Justification of Design

This trial employs an optimal Simon two-stage design with a= 0.05, assuming that the treatment is not worthy of further consideration if the probability of patients achieving a positive outcome (at least partial response and PFS 6 months) is less than 0.1. The design has 90% power if the true probability of positive outcome is 0.3 or greater. The stopping rule is designed to pause the trial if P(P[DLT > 0.3] > 0.7), using a beta-binomial model with a=1 and =4; that is, our prior expectation based on information equivalent to a total of five patients is that the P(DLT) = 0.2. The operating characteristics of the stopping rule, derived from a Monte Carlo simulation, are presented in the figure, where it is seen that, for instance, if the true probability of DLT is 0.3, the probability that the trial pauses is 0.4 and the expected number of participants accrued is 12.

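### The DLT boundary is applied only at blocks of five, so participants can still be started after the next row's count has been reached; a one-sentence curtailment would prevent this, with a modest benefit

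*Combined protocol and SAP*

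**What the plan says.** Section 8.2.4, under a heading about biomarkers, holds the DLT rule: "a stopping rule will be evaluated after every five participants have started Cycle 1". The action is stated as: "If the number of participants experiencing DLT equals or exceeds the number specified in the following table, the trial will be paused and the dosing" (the sentence ends by saying that dosing is then looked at again). The rows are 3 DLTs in 5 participants, 5 in 10, 7 in 15, 8 in 20, 10 in 25 and 12 in 30.

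The Protocol Summary also uses blocks of five but times the look differently: "A formal, sequential decision rule based on dose-limiting toxicity will be evaluated after every five participants have completed Cycle 1". The DLT window in section 8.1.1 runs "from first dose through completion of the first 28-day cycle".

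Section 8.3 gives the basis of the rule: "The stopping rule is designed to pause the trial if P(P[DLT > 0.3] > 0.7". The prior is stated in the same place, in these terms: "using a beta-binomial model with a=1 and =4". Section 8.3 also gives one operating characteristic: "if the true probability of DLT is 0.3, the probability that the trial pauses is 0.4 and the expected number of participants accrued is 12". Maximum accrual is in the Protocol Summary: "Eighteen in the first stage and seventeen in the second stage, for a maximum of 35 patients".

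Sections 7.5 and 8.2.4 provide for continuing safety monitoring, and section 9.4 lets the monitoring bodies suspend accrual. None of them states a DLT count that triggers action between rows.

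**The concern.** The rule looks at a cumulative count, and that count can only rise. If the first three participants all have a DLT, the first row (3 in 5) is already met, and participants 4 and 5 cannot change the decision. As written, the rule is not evaluated until the block of five is reached, so those two may still be started. They would receive a combination that the trial's own criterion has already committed to pausing, and their outcomes add nothing to that decision.

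At stake is avoidable exposure of a small number of participants in trials that pause, and a delay in reaching the pause.

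**Working it through.** **Inputs.** Six rows (section 8.2.4); Beta(1,4) prior and the 0.3 and 0.7 cutoffs (section 8.3); maximum 35 participants and 12 months of enrollment (Protocol Summary); 28-day DLT window (section 8.1.1).

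**1. Reproduce the table.** The criterion is read as: pause if P(p > 0.3 | x DLTs in n) > 0.7, with posterior Beta(1 + x, 4 + n − x).

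| n | row x | posterior at x | posterior at x − 1 |
|---|---|---|---|
| 5 | 3 | 0.730 | 0.463 |
| 10 | 5 | 0.781 | 0.584 |
| 15 | 7 | 0.818 | 0.666 |
| 20 | 8 | 0.725 | 0.565 |
| 25 | 10 | 0.771 | 0.636 |
| 30 | 12 | 0.807 | 0.693 |

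All six rows reproduce.

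**2. Reproduce the stated operating characteristic.** An exact recursion on the binomial count at p = 0.3 gives first-pause probabilities of 0.1631, 0.0618, 0.0322, 0.0733, 0.0237 and 0.0138 at looks 5 to 30. They sum to 0.368, which rounds to the stated 0.4. Mean accrual given a pause is (5 × 0.1631 + 10 × 0.0618 + 15 × 0.0322 + 20 × 0.0733 + 25 × 0.0237 + 30 × 0.0138) / 0.368 = 11.9, the stated 12. Over all trials it is 4.39 + 35 × 0.632 = 26.5, so the stated 12 describes paused trials only.

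**3. Curtail.** The same recursion is used, but the trial pauses as soon as the count reaches the number for the next row. Full Cycle 1 outcomes are counted in enrollment order, and accrual is assumed to reach the next row.

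| True DLT rate | P(pause), both rules | Mean n at pause, block | Mean n at pause, curtailed |
|---|---|---|---|
| 0.2 | 0.094 | 9.2 | 8.6 |
| 0.3 | 0.368 | 11.9 | 11.2 |
| 0.4 | 0.740 | 12.0 | 11.2 |
| 0.5 | 0.949 | 10.0 | 9.1 |

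The saving is 0.6 to 0.9 participants per pause. At p = 0.3 it is 26.51 − 26.25 = 0.26 over all trials. In 400,000 simulated paths at p = 0.3 the two rules never disagreed on whether to pause. About 49% of pauses saved nobody, 33% saved one, 16% two and 2% three.

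**4. Add calendar time.** Assumptions: 35 participants accrued over 12 months at a constant rate (2.92 per month), DLT onset uniform over Cycle 1, and block looks when Cycle 1 is completed. Participants started by the time of the pause fall from 14.6 to 12.7 (p = 0.3), 14.6 to 12.6 (0.4) and 12.7 to 10.5 (0.5). The pause comes about 20 to 22 days earlier.

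**5. Where the pause probability changes.**

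- *Literal start-of-cycle look.* When the fifth participant of a block starts, the latest entrants have little of their 28-day window behind them. Their later DLTs are first counted at the next, higher row. Under the step 4 accrual and onset assumptions, with random arrivals, the pause probability goes from about 0.22 (literal) to 0.37 (curtailed) at p = 0.3, 0.58 to 0.74 at 0.4, and 0.88 to 0.95 at 0.5.
- *Trial ending at 18 for futility.* The block rule never reaches the look at 20, but the curtailed rule can act on that row during participants 16 to 18. At p = 0.3 the probability goes from 0.257 to 0.280.

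**The case against.** The strongest case against is that nothing in the block design is an error. The table follows exactly from the stated criterion, and cohort looks are an ordinary choice. The documents also leave room to act sooner: DLTs are monitored throughout (8.2.4), safety data are reviewed on an ongoing basis (7.5), section 3.1 provides for de-escalation if monitoring suggests intolerance, section 3.3 for termination for unacceptable risk, and section 9.4 for suspension of accrual. A reader might infer that the protocol obliges sites to keep enrolling after, say, three DLTs in three participants. It does not say that. What is missing is only a numeric trigger between rows. That gap is real, because discretion is not the pre-specified boundary that the rule exists to provide.

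A reader might also infer that curtailing leaves the pause probability exactly the same in all circumstances. The documents do not support this. It holds for looks at completed Cycle 1 with accrual reaching the next row, and fails in the two cases of step 5. In both, the extra pauses occur because a row's DLT count has been reached and is acted on. In the first, the probability moves from about 0.22 to 0.37, which agrees with the stated 0.4.

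The size objection stands. The saving by enrollment order is below one participant per pause on average, and the figure of about two rests on assumed accrual, onset and end-of-cycle looks. Constant accrual is doubtful, since the stage 1 decision needs six-month outcomes on 18 participants and the plan does not say whether enrollment continues meanwhile.

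Finally, curtailment is not the same as applying the posterior criterion after every participant. That would raise the pause probability at p = 0.3 to 0.480 and would be a different rule.

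**Conclusion.** The concern holds as a cheap improvement, not as an error in the boundary. The written rule lets participants be started after the pause at the next row is determined, and no section supplies a trigger to prevent it. The benefit is modest: 0.6 to 0.9 fewer participants per pause by enrollment order for true DLT rates of 0.2 to 0.5, and at most three in any trial. It is about two per pause only under the calendar-time assumptions.

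That the count cannot fall does not depend on those assumptions. Equality of the pause probability does depend on how the two timing statements are reconciled and on accrual reaching the next row. Neither version of the rule covers participants 31 to 35, because the table has no row beyond 30.

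**What to change.** 1. Keep the table, prior and cutoffs.
2. Reconcile section 8.2.4 (looks when Cycle 1 has started) with the Protocol Summary (looks when Cycle 1 is completed).
3. Add to section 8.2.4: *Accrual pauses as soon as the number of DLTs among the first n participants reaches the number in the row for n, without waiting for the remaining participants of that block.* A short clause should note that this can also act on the row for 20 in a trial that ends at 18.
4. In section 8.3, label the expected accrual of 12 as conditional on a pause and update it to about 11.

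The cost is one sentence plus the timing reconciliation. Pauses come slightly earlier. If looks are at completed Cycle 1 and accrual reaches the next row, the stated pause probability does not change.
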